6.1.1 Overview of Treatment-Emergent Adverse Events

Analysis Set:	Safety An	alysis Set	
Analysis			
Variable(s) :	TEAE		
Categories:	Relationsh	ip to Study Drug	[Related, Not Related]
	Intensity		[Grade 1, Grade 2, Grade 3, Grade 4, Grade 5]
Analytical			
Method(s) :	The follow	ving summaries wil	l be provided for each treatment group.
	TEAEs wi	ll be graded using t	he National Cancer Institute-Common
	Terminolo	gy Criteria for Adv	verse Events (CTCAE) Version 4.03.
	(1) Ove	erview of Treatmen	t-Emergent Adverse Events
	1)	All Treatment-Em	nergent Adverse Events (number of events,
		number and perce	ntage of subjects)
	2)	Relationship of T	reatment-Emergent Adverse Events to study
		drug (number of e	events, number and percentage of subjects)
	3)	Intensity of Treat	nent-Emergent Adverse Events (number of
		events, number an	d percentage of subjects)
	4)	Treatment-Emerg	ent Adverse Events leading to study drug
		discontinuation (n	umber of events, number and percentage of
	subjects)5) Serious Treatment-Emergent Adverse Events (number of events)		
			t-Emergent Adverse Events (number of events,
		number and perce	ntage of subjects)
	6)	Relationship of se	rious Treatment-Emergent Adverse Events to
		study drug (numb	er of events, number and percentage of subjects)
	7)	Serious Treatmen	t-Emergent Adverse Events leading to study
		drug discontinuati	on (number of events, number and percentage of
		subjects)	
	8)	Treatment-Emerg	ent Adverse Events resulting in death (number
		of events, number	and percentage of subjects)
	TEAEs wi	ll be counted accor	ding to the rules below.
	Number of	f subjects	
	• Summ	aries for 2) and 6)	
	A subje	ct with occurrences	of TEAE in both categories (i.e., Related and

Not Related) will be counted once in the Related category.

• Summary for 3)

A subject with multiple occurrences of TEAE will be counted once for the TEAE with the maximum intensity.

• Summaries other than 2), 3), and 6)

A subject with multiple occurrences of TEAE will be counted only once. Number of events

For each summary, the total number of events will be calculated.

6.1.2 Displays of Treatment-Emergent Adverse Events

Analysis Set:	Safety Analysis Set	
Analysis		
Variable(s) :	TEAE	
Categories:	Intensity	[Grade 1, Grade 2, Grade 3, Grade 4, Grade 5]
	Time of Onset (day)	[1<= - <=90, 91<= - <=180, 181<= - <=270,
		271<=-<=360, 361<=-<=450, 451<=-<=540,
		541<= - <=630, 631<= - <=Max]

Analytical

Method(s): The following summaries will be provided using frequency distribution for each treatment group.

TEAEs will be coded using the MedDRA and will be summarized using SOC and PT. SOC will be sorted alphabetically and PT will be sorted in decreasing frequency for tables provided by SOC and PT. SOC and PT will be sorted in decreasing frequency for tables provided by System Organ Class only or PT only.

TEAEs will be graded using the National Cancer Institute-Common Terminology Criteria for Adverse Events (CTCAE) Version 4.03.

- Treatment-Emergent Adverse Events by System Organ Class and Preferred Term
- (2) Treatment-Emergent Adverse Events by System Organ Class
- (3) Treatment-Emergent Adverse Events by Preferred Term
- (4) Drug-Related Treatment-Emergent Adverse Events by System Organ Class and Preferred Term
- (5) Drug-Related Treatment-Emergent Adverse Events by Preferred Term
- (6) Intensity of Treatment-Emergent Adverse Events by System Organ Class and Preferred Term

- (7) Intensity of Drug-Related Treatment-Emergent Adverse Events by System Organ Class and Preferred Term
- (8) Treatment-Emergent Adverse Events with Intensity of Grade 3 or Higher by System Organ Class and Preferred Term
- (9) Treatment-Emergent Adverse Events Leading to Study Drug Discontinuation by System Organ Class and Preferred Term
- (10) Serious Treatment-Emergent Adverse Events by System Organ Class and Preferred Term
- (11) Treatment-Emergent Adverse Events by System Organ Class and Preferred Term Over Time
- (12) Special Interest Treatment-Emergent Adverse Events by System Organ Class and Preferred Term

The frequency distribution will be provided according to the rules below. Number of subjects

• Summary tables other than (6), (7), (8), and (11)

A subject with multiple occurrences of TEAE within a SOC will be counted only once in that SOC. A subject with multiple occurrences of TEAE within a PT will be counted only once in that PT. Percentages will be based on the number of subjects in the safety analysis set.

• Summary tables for (6), (7), and (8)

A subject with multiple occurrences of TEAE within a SOC or a PT will be counted only once for the TEAE with the maximum intensity. Percentages will be based on the number of subjects in the safety analysis set.

• Summary table for (11)

A subject with a TEAE that occurs in more than one interval is counted in all the intervals that the TEAE occurs. For each time interval, a subject with multiple occurrences of TEAE within a SOC or a PT will be counted only once in that SOC or PT.

When calculating percentages for each time interval, the number of subjects at risk (i.e., subjects who either have an exposure or have an occurrence of TEAE, during or after the corresponding time interval) will be used as the denominator. The number of subjects whose onset of any one of the TEAEs is within the time interval will be used as the numerator.

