Study Design: 
This study consists of two parts: Part A, a dose-rising phase, and Part B, an expansion phase.
 
In Part A, three to six patients will be enrolled in each cohort. Whether or not the study will proceed to the next cohort or Part B will be determined through assessment of tolerability at the dose in question, based on the incidence of dose-limiting toxicity (DLT) in the evaluation period. TAK-385 will be taken once a day for 28 days at the doses assigned to each cohort. Cohort 1 will receive a loading dose of 320 mg and a maintenance dose of 80 mg, Cohort 2 will receive a loading dose of 320 mg and a maintenance dose of 120 mg, Cohort 3 will receive a loading dose of 320 mg and a maintenance dose of 160 mg, and Cohort 4 will receive a loading dose of 360 mg and a maintenance dose of 120 mg. Patients being switched to a gonadotropin-releasing hormone (GnRH) agonist (eg, leuporelin) or a GnRH antagonist (eg, degarelix) following the completion of TAK-385 treatment in Part A will first pass through a 1-week observation period (except for study withdrawals). Whether or not the study will proceed to Part B will be determined by the study sponsor after consulting the study monitoring committee (SMC) based on a comprehensive evaluation of the tolerability and safety data from Cohort 2 of Part A.
 
In Part B, subjects will be randomized to receive study drug (TAK-385 loading dose of 320 mg and maintenance dose of either 80 mg or 120 mg – equal numbers of subjects will be randomized to 80 mg and 120 mg) once a day orally to evaluate safety. In addition to the safety assessments, efficacy assessments will also be performed according to the study schedule, and study drug will be administered until the discontinuation criteria (Section 7.5) are met for each individual subject. After completing 48 weeks of treatment, subject may, at the discretion of the investigator, and depending on the wishes of the subject, continue receiving study drug (for a maximum of 96 weeks), or they may complete the study and be switched to a GnRH agonist or a GnHR antagonist, starting from the day after the day of the last dose of TAK-385.
 
All subjects who receive study drug will undergo safety follow-up 30 to 40 days after the last dose of TAK-385.
		

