## 10.2 Procedures

### 10.2.1 Collection and Reporting of Adverse Events

#### 10.2.1.1 Collection Period of Pretreatment Events and Adverse Events

Pretreatment events will be recorded continuously from when informed consent is obtained until the first dose of study drug (Day 1). If it is decided that a subject should be withdrawn before the first dose of study drug, PTEs will be recorded until that point in time.

AEs will be recorded continuously from the start of study drug administration to subjects (Day 1) until the safety follow-up.

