**Appendix C Schedule of Study Procedures (Part B – Weeks 49 to 96)**

Procedure a	Continuation Treatment Period b					Withdrawal	SFU
	WK49 (WK48) D1 (D8)	WK61 D1	WK73 D1	WK85 D1	WK97 c D1		30 to 40 days after the last dose
Visit Day Allowable Window	±7	±7	±7	±7	±7	+7	
Physical examination	X	X	X	X	X	X	X
Vital signs d	X	X	X	X	X	X	X
Weight	X	X	X	X	X	X	X
ECOG performance status	X	X	X	X	X	X	X
12-lead ECG e	X		X		X	X	X
Imaging assessment	X				X	X	
Bone density (DXA method)	X		X		X	X	
Hematology tests	X	X	X	X	X	X	X
Blood biochemistry tests	X	X	X	X	X	X	X
Blood lipid, sugar, etc. tests	X	X	X	X	X	X	X
Urinalysis	X	X	X	X	X	X	X
Pharmacodynamic assessments	X	X	X	X	X	X	
Tumor marker	X	X	X	X	X	X	
QOL assessments	X	X	X	X	X	X	X
Concomitant medications/ therapies	Information collected until 30 to 40 days after the last dose						
Adverse events, etc.	Information collected until 30 to 40 days after the last dose						
treatment	Oral doses once a day at least 30 minutes before breakfast f						

Abbreviations: WK = Week; D = Day; ECOG = Eastern Cooperative Oncology Group; QOL = quality of life; SFU = safety follow-up

- a Unless otherwise specified, the assessments will be completed before study drug dosing.  
 b Additional examinations/assessments may be performed at the discretion of the investigator or sub-investigator.  
 c If a subject is going to be switched to a GnRH agonist or a GnRH antagonist, this will be done after PK analysis sample collection and assessments have been completed.  
 d Measurements will be taken after the subject has been sitting down for 5 minutes.  
 e Measurements will be taken after the subject has been lying down for 5 minutes.  
 f Study drug will not be taken at WK97D1.

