WK73D1	Study Day: 505	463 - 546	< 15
WK85D1	Study Day: 589	547 - 630	< 15
WK97D1	Study Day: 673	631 - 687	< 15
SFU	Follow-up Day: 40		15 - 40

	Scheduled Study Day	Time Interval (days)	
Visit	(days)	Study Day	Follow-up Day
Baseline (Week 0)	Study Day: 1	-28 - 1	
WK3D1	Study Day: 15	2 - 21	< 15
WK5D1	Study Day: 29	22 - 98	< 15
WK25D1	Study Day: 169	99 – 252	< 15
WK49D1	Study Day: 337	253 - 420	< 15
WK73D1	Study Day: 505	421 - 588	< 15
WK97D1	Study Day: 673	589 - 687	< 15
SFU	Follow-up Day: 40		15 - 40

12-Lead Electrocardiogram

Vital Signs, Weight

	Scheduled Study Day	Time Interval (days)	
Visit	Visit (days)		Follow-up Day
Baseline (Week 0)	Study Day: 1	-28 - 1	
WK2D1	Study Day: 8	2 - 11	< 15
WK3D1	Study Day: 15	12 - 21	< 15
WK5D1	Study Day: 29	22 - 42	< 15
WK9D1	Study Day: 57	43 - 70	< 15
WK13D1	Study Day: 85	71 - 126	< 15
WK25D1	Study Day: 169	127 - 252	< 15
WK49D1	Study Day: 337	253 - 378	< 15
WK61D1	Study Day: 421	379 - 462	< 15
WK73D1	Study Day: 505	463 - 546	< 15
WK85D1	Study Day: 589	547 - 630	< 15
WK97D1	Study Day: 673	631 - 687	< 15
SFU	Follow-up Day: 40		15 - 40

Visit	Scheduled Study Day (days)	Time Interval (days) Study Day
Baseline (Week 0)	Study Day: 1	-28 - 1
WK25D1	Study Day: 169	2 - 252
WK49D1	Study Day: 337	253 - 420
WK73D1	Study Day: 505	421 - 588
WK97D1	Study Day: 673	589 - 713

Bone Mineral Density (DXA)

Others

- Duration of exposure to study drug (days) : date of last dose of study drug date of first dose of study drug + 1
- Dose intensity (mg/day): total amount of doses taken / duration of exposure to study drug (rounded to 1 decimal place)
- Relative dose intensity (%): (total amount of doses taken / total dose expected per initial dose) * 100 (rounded to 1 decimal place)
- Dosing compliance: (total amount of doses taken / total dose expected) * 100 (rounded to 1 decimal place)
- Disease duration (days): date subject signed Informed Consent Form date of diagnosis + 1
 - For the date subject signed Informed Consent Form, the year, the month, and the day will be used for the calculation.
 - If the year is unknown, then the date of diagnosis will be treated as missing. If the month is unknown, then the month will be treated as January and the day will be treated as the 1st day of the month. If only the day is unknown, then the day will be treated as the 1st day of the month for the calculation.
- PK parameters:
 - AUC_{last} --Area under the concentration-time curve from time 0 to time of the last quantifiable concentration.

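### SAP table (11): once off drug, a subject counts as at risk only if he has a TEAE, so the denominator depends on the outcome (mainly Part B, Day 361–450; low severity)

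*SAP*

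**What the plan says.** SAP 6.1.2 (Part B), in the rule for summary table (11), takes as denominator the "subjects who either have an exposure or have an occurrence of TEAE, during or after the corresponding time interval". SAP 5.1.2 uses the same wording for Part A. The numerator is given as follows: "The number of subjects whose onset of any one of the TEAEs is within the time interval will be used as the numerator". The rule opens with a third phrasing: "A subject with a TEAE that occurs in more than one interval is counted in all the intervals that the TEAE occurs".

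The Part B onset categories are 90-day bins, including "271<=-<=360, 361<=-<=450, 451<=-<=540"; the last runs from Day 631 upward. The last Part A category starts at Day 22 and has no upper limit.

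Exposure is bounded by dosing. The SAP's list of derived variables begins its definition "Duration of exposure to study drug (days) : date of last dose of study drug" and subtracts the date of first dose, plus 1. AE collection goes on longer. Protocol 10.2.1.1: "AEs will be recorded continuously from the start of study drug administration to subjects (Day 1) until the safety follow-up". Protocol 2.0: "All subjects who receive study drug will undergo safety follow-up 30 to 40 days after the last dose of TAK-385". The SAP glossary defines a TEAE by onset on or after the start of study drug, with no cut-off at the last dose.

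**The concern.** Take two subjects who are both off drug and both still under AE collection when an interval opens. The one with a later TEAE is counted in numerator and denominator. The one without is in neither. Membership of the risk set is thus decided by the outcome being measured, and no other text in the protocol or SAP brings the event-free subject back.

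The resulting percentage is neither a risk on drug nor a risk over the period in which AEs were observed. This matters because AEs are a primary endpoint, protocol 13.1.7 asks for TEAEs by time of onset, and table (11) is the only TEAE display by time. It is also the only display in 6.1.2 whose percentages are not based on the whole safety analysis set.

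**Working it through.** **The plan's own figure.** None is given for this table. The one Part B sample-size figure (protocol 13.3) is a chance of about 80% of seeing an AE with 10% true incidence: 1 − 0.9^15 = 0.794. This reproduces for one group of 15, the group size used below.

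**Day count, Part B.** Week 49 Day 1 is Study Day 337 (SAP visit windows), so a subject who stops at Week 48 has a nominal last dose on 48 × 7 = Day 336.
- Follow-up falls on Day 336 + 30 = 366 to 336 + 40 = 376, which puts 6 to 16 days in the 361–450 bin with no exposure in it.
- The row "Visit Day Allowable Window" in protocol Appendix C gives ±7 days at Week 49. If the last dose is the day before that visit, it lies on Day 329–343. Follow-up then ends between 329 + 30 = Day 359 and 343 + 40 = Day 383, giving 0 to 23 days in the bin.
- Week 96 completers (last dose Day 672, follow-up Day 702–712) stay within the bin from Day 631.
- Early discontinuers are affected if the last dose is at most 40 days before a bin opens, for example Day 51–90 for the bin opening on Day 91.

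**Day count, Part A.** Completers (last dose Day 28, follow-up Day 58–68) stay within the bin from Day 22. Only subjects who stop before Day 22 are affected.

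**Size in Day 361–450.** Assumptions not in the documents: constant hazard of 0.3 per 90 days, also in follow-up; *c* of 15 continue; 11 follow-up days (midpoint of 6–16); *occurrence* means onset.
- On-drug risk over 90 days: p = 1 − exp(−0.3) = 25.9%.
- Follow-up risk: q = 1 − exp(−0.3 × 11/90) = 3.6%.
- With a ~ Bin(c, p) and b ~ Bin(15 − c, q), the table shows (a + b)/(c + b). Exact expectation:

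| Continuing | Any-TEAE %, 11 days (0–23 days) | Shift from 25.9% | SD | P(≥1 stopper has an onset), 11 days |
|---|---|---|---|---|
| 12 | 26.5 (25.9–27.2) | +0.6 | 13 | 10.4% |
| 8 | 27.9 (25.9–30.0) | +2.0 | 16 | 22.6% |
| 4 | 31.4 (25.9–36.6) | +5.5 | 22 | 33.2% |

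At a hazard of 0.1 (on-drug risk 9.5%) the figures are 9.8 (9.5–10.0), 10.4 (9.5–11.3) and 11.9 (9.5–14.3)%. If all 15 continue, Week 48 stops add nothing.

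**Direction.** Because a ≤ c, (a + b)/(c + b) is never below a/c in the any-TEAE row. The denominator is shared across rows, so a single-PT row can fall: 1/8 = 12.5% becomes 1/9 = 11.1% if the stopper's TEAE has a different PT.

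**Candidate remedies, same assumptions (12, 8, 4 continuing).**
- Plain percentage over all observed subjects: (c·p + (15 − c)·q)/15 = 21.5, 15.5, 9.6%. It falls only because 11 days are mixed with 90.
- On-treatment counts, with later TEAEs in a separate column: in the 271–360 bin a stopper now contributes 66 of 90 days (Day 271–336), with risk 1 − exp(−0.3 × 66/90) = 19.7%. The bin shows 24.7, 23.0, 21.4% instead of 25.9%, and it was sound before.
- Subjects with an onset per subject-time observed: (c·p + (15 − c)·q) / (90c + 11(15 − c)) is 3.22/1113, 2.33/797 and 1.43/481 per day, or 26.0, 26.3, 26.8 per 100 subject-periods of 90 days. It is nearly constant. The small drift arises because time is not stopped at the first onset.

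**The case against.** The case against acting concerns weight. The table is descriptive, no test or cohort-advancement rule uses it, and the other eleven TEAE displays are untouched. The expected shift is well inside the SD, and its size cannot be known from the documents, which do not say how many subjects stop at Week 48. SAP 2.1.5 and 2.3.1 tabulate exposure with the same interior cut-points, so a reader can recover the on-drug number per bin and, under the onset reading, the on-drug any-TEAE count (not the SOC or PT counts). The clause does at least keep the numerator inside the denominator. The separate data-handling rules, which are not supplied, might define exposure differently. All of this stands and sets the severity. None of it makes the denominator independent of the outcome.

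A reader might go further and infer from the mixed use of *occurs*, *occurrence* and *onset* that a TEAE merely ongoing in the interval also admits a stopper, so that the distortion could vanish or reverse. The documents give little support for this. The numerator is by onset, protocol 13.1.7 asks for time of onset, and elsewhere the SAP speaks of occurrences when it counts reported events. A TEAE in more than one interval fits recurrence, or a worsening recorded as a separate AE (protocol 10.1.6). The wording should be aligned, but the point does not rest on that reading.

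**Conclusion.** The at-risk rule is wrong as written, at low severity. The mechanism follows from the text alone. The location is mainly Day 361–450 in Part B for Week 48 stoppers, and otherwise only early discontinuers whose follow-up crosses a bin boundary. The size rests on the assumed hazard, follow-up days and number continuing. It reaches several points only if most subjects stop at Week 48.

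Two stronger conclusions are not supported. A reader might set the rule against all 15 subjects and infer gross inflation: with 10 continuing (4 with a TEAE) and 5 stopping (1 with a TEAE), 5/11 = 45.5% against 5/15 = 33.3%. That comparator gives 6–16 days the same weight as up to 90, so the gap is not a measure of bias; the on-drug figure is 4/10 = 40.0%. A reader might also infer that the primary safety results are biased. The defect is confined to this one table, and the other TEAE percentages in 6.1.2 use the safety analysis set.

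**What to change.** In SAP 5.1.2 and 6.1.2, rule for table (11):
- Keep the calendar-day onset bins and all TEAEs.
- Delete the TEAE-occurrence alternative from the at-risk definition. Define at risk as being under AE observation in the interval, from first dose to safety follow-up or last contact, whatever the outcome.
- For each interval report the number of subjects with an onset, the subject-time under AE observation and the rate per subject-time. State whether time stops at a subject's first onset in the interval.
- In the rule's first sentence, refer to a TEAE having an onset in an interval, to match the numerator and protocol 13.1.7.

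Do not instead move TEAEs after the last dose to a separate follow-up column beside on-treatment subject counts. That understates Day 271–360, as shown, and takes follow-up onsets out of the last Part A and last Part B bins, which are sound for completers.

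The cost is two sentences in each section, a small programming change, and a rate shown beside or in place of the percentage. The dates of first dose, last dose and AE onset are already collected, safety follow-up status is already tabulated (SAP 2.1.4 for Part B), and no other TEAE display changes.

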6.2 Pretreatment Events

6.2.1 Displays of Pretreatment Events

Analysis Set: All Subjects Who Signed the Informed Consent Form Analysis

Variable(s) : PTE

Analytical

Method(s):The following summaries will be provided using frequency distribution.PTEs will be coded using the MedDRA and will be summarized using SOCand PT. SOC will be sorted alphabetically and PT will be sorted in decreasingfrequency.

(1) Pretreatment Events by System Organ Class and Preferred Term

(2) Serious Pretreatment Events by System Organ Class and Preferred Term Number of subjects

A subject with multiple occurrences of PTE within a SOC will be counted only once in that SOC. A subject with multiple occurrences of PTE within a PT will be counted only once in that PT.

6.3 Laboratory and Other Safety Data

6.3.1 Laboratory Test Results

6.3.1.1 Hematology, Biochemistry, and Lipid and Glycated Hemoglobin in Blood

Analysis Set: Safety Analysis Set

Analysis

Variable(s): Hematology

	Red Blood Cell	White Blood Cell	Hemoglobin
	Hematocrit	it Platelets	
	Differential WBC (Neutr	ophils, Neutrophil Count, I	Basophils, Eosinophils,
	Lymphocytes, Monocyte		
	Biochemistry		
	Protein Total	Albumin	Glucose
	Creatinine	Blood Urea	Uric Acid
		Nitrogen	
	Bilirubin Total	ALT (GPT)	AST (GOT)
	LDH	GGT	Alkaline Phosphatase
	СК (СРК)	Sodium	Potassium
	Chloride	Calcium	Corrected Calcium
	Phosphorus	PT-INR	
	Lipid and Glycated Hemogl	obin in Blood	
	Triglycerides	Total Cholesterol	HDL Cholesterol
	LDL Cholesterol	TSH	HbA1c
Categories:	Intensity [Grade 0, Grade 1, Grade 2, Grade 3, Grade 4]		
Visit:	(1) and (2):		
	Hematology: Baseline, WK	5D1, WK9D1, WK13D1, V	WK25D1, WK37D1,
	WK49D1, WI	K61D1, WK73D1, WK85D	01, WK97D1, SFU
	Biochemistry: Baseline, WI	K5D1, WK9D1, WK13D1,	WK17D1, WK21D1,
	WK25D1, W	K29D1, WK33D1, WK37	D1, WK41D1,
	WK45D1, WK49D1, WK61D1, WK73D1, WK85D1,		
	WK97D1, S		
	Lipid and Glycated Hemogl		
		5D1, WK9D1, WK13D1, V	
	WK61D1, WI	K73D1, WK85D1, WK97D	01, SFU
Analytical			
Method(s) :	For each variable, summarie		
	For applicable variables, sur		1
	treatment group. Takeda Pro	eferred SI Units will be use	d for all summaries.

 Summary of Laboratory Test Results and Change from Baseline by Visit

Descriptive statistics for observed values and changes from baseline will be provided for each visit.

(2) Case Plots

Plots over time for each subject will be presented.

 (3) Number and Percentage of Subjects with Elevated Liver Enzyme Laboratory Parameters
 Overall frequency distributions of elevated hepatic parameters will be

provided. Further details are given in Appendix.

(4) Number and Percentage of Subjects with Laboratory Test Abnormalities by Grade

Frequency distributions for each laboratory test abnormality will be provided by grade. Evaluable data (i.e., non-missing and acceptable according to the Handling Rules for Analysis Data) obtained after baseline will be used. A subject with multiple occurrences of laboratory test abnormality will be counted once for the abnormality with the maximum intensity.

(5) Maximum Grade Shift From Baseline of Laboratory Parameters The maximum post-baseline grade will be determined for each subject. Shift tables showing the number of subjects in each grade category at baseline and post-baseline visit will be provided using evaluable data (i.e., non-missing and acceptable according to the Handling Rules for Analysis Data).

